Brief Admission (BA – Brukarstyrd inläggning) is in this project defined as the specific intervention, standardized by the Brief Admission Skåne Fidelity Measure (BASF, Bilaga 2b; Liljedahl, Helleman, Daukantaite & Westling, 2017). *Brief Admission Skåne (BAS - Brukarstyrd inläggning Skåne)* is the randomized controlled trial evaluating the intervention.

General Admission (GA – Läkarstyrd inläggning) is defined as all other admissions, voluntary as well as coercive, to the emergency ward (psychiatric or somatic) due to psychiatric needs or following an act of self-harm or a suicide attempt, including possible following days with hospital admission.

Patient selection criteria

Inclusion criteria:

- Current episodes of self-harm and/or recurrent suicidality.

- Fulfilling at least three criteria for Borderline Personality Disorder.
- Admitted to hospital care for at least 7 days or presenting to the psychiatric emergency department at least 3 times during the last six months.
- Age 18-60 years.

Exclusion criteria:

- No current ambulatory clinician
- No current place to live (homeless).
- Medical disorder from other organs that significantly contributes to symptoms (e.g. if self-harm only occurs during episodes of hypoglycemia in a diabetic patient).

Testing for autism, attention deficit or learning disabilities exceed the scope of this study. These diagnoses are not considered to be exclusion criteria, neither are they related in a more direct way to any of the research objectives. Thus, since the proposed assessments already are considerably time-consuming (see justification for measures, below), testing for these diagnoses is excluded.

Methods of evaluation (Figure 1, Bilaga 2c and Bilaga 5a-j)

Data collected from hospital records

From local hospital records, data is collected concerning:

- Number of days with general admission to hospital
- Visits at the psychiatric emergency department,
- Whether the admission was voluntary or coercive
- Coercive acts as defined by LPT; 1991:1128: §19, 20, 21, 22, 23 and 24.

Hospital data are collected monthly retrospectively from twelve months before the intervention start of the pilot and until endpoint after 12 months of the active study period. This generates quantitative data registered in a form (Bilaga 5a).

Justification for Measures

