All participants randomized to the intervention during the pilot phase as well as the 10% of the individuals with the highest number of days admitted to hospital 12 months before baseline, will be selected for Time-Series Design (TS). The TS will follow an A-B replication case-series design where the number of days of GA to hospital will be monitored monthly, retrospectively with data from the local hospital records, from one year ahead of assigning to the study (A) and during the time the participant is allocated to either BA+TAU or TAU (one year; B).

Testing Schedule

For a visual description of the testing schedule, please see Figure 1, Bilaga 2c.

1. Individuals with symptoms suggesting that they may fulfill inclusion criteria, are asked by any clinician at the current department, if they want to participate in the study. If the individual is interested in participating, the clinician passes contact information to the PI.
2. PI checks if the inclusion criteria seem to be fulfilled and no exclusion criteria.
3. PI provides written and verbal information about the study, including time for questions and asks the individual to sign the consent form.
4. PI registers the participant in the screening log and provides a consecutive research number.
5. PI performs assessments with:
 - a. M.I.N.I. 7.0.0 (Sheehan, Lecriubier, Harnett-Sheehan, Janavs, Weiller, Bonara, Kesker, Schinka, Knapp, Sheehan & Dunbar, 1997; Lecriubier, Sheehan, Weiller, Amorim, Bonara, Sheehan, Janavs & Dunbar, 1997)
 - b. SCID II (First, Gibbon, Spitzer, Williams & Benjamin, 1998)
 - c. Fem frågor (Holmqvist & Nylander, 2013a),
 - d. AUDIT (Saunders, Aasland, Babor, Delafuente, Grant, 1993; Babor, Higgins-Biddle, Saunders & Monteiro, 2001)
 - e. DUDIT (Berman, Bergman, Palmstierna & Schlyter, 2005).
6. PI provides a consecutively numbered randomization envelope which the participant opens and signs. This is registered in the randomization log. According to which

group the participant is enrolled in, a sheet providing information on the study is given and explained.

7. Data collection at baseline by PI:
 - a. For the individuals randomized to the control group, data from hospital records for the previous 12 months, and CGI-S (Guy, 1976), are recorded with baseline date on the day for the randomization.

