 - b. For individuals randomized to the intervention group data from hospital records and CGI-S (Guy, 1976), are recorded with baseline date on the day for the contract (i.e. day when BA is accessible).
8. Data collection at baseline by a Research Assistant (RA):
 - a. After randomization PI contacts a local RA who schedules an appointment with all participants, and administers a link to the self-administered forms:
 - i. 5S-HM (Liljedahl & Westling, 2014),
 - ii. WHODAS 2.0 (WHODAS 2.0; 2014),
 - iii. Brief COPE (Carver, 1997; Muñoz & Torkelson, 2005), DERS (Gratz & Roemer, 2004; Friberg, 2006),
 - iv. ISAS (Klonsky & Glenn, 2009; Glenn & Klonsky, 2011; Lindholm, Bjärehed & Lundh, 2011).
 - b. RA is available for the individual and provides help if necessary, when completing the forms online.
 - c. For individuals randomized to the intervention group RA further contacts their primary clinician as well as ward staff at the ward providing BA, to schedule an appointment for negotiation resulting in a BA contract. At the end of the negotiation IES and CES (negotiation part) are completed online.
9. Data collection at 6 and 12 months (± 2 weeks) is repeated as baseline, with the change that the contract negotiation is replaced by contract evaluation for the intervention group and data from hospital records is collected from the previous 6 months.

Pilot phase

The first three months of the study (Sept, 2015 – Jan, 2016) will form a pilot phase with the goal of optimizing the intervention, evaluate the inclusion and exclusion criteria and preliminary testing to determine whether the quality and quantity of assessments are adequate and feasible. At the termination of the pilot phase evaluation with IES and CES (Liljedahl, Helleman, Daukantaite & Westling, 2017) will be performed.

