 - Outcome is data from IES and the CES (Liljedahl, Helleman, Daukantaite & Westling, 2017) completed by the participants and clinicians administering BA after pilot testing, 6 and 12 months
8. Can the *Five Self-Harm Behaviour Groupings Measure* (5S-HM: Liljedahl & Westling, 2014) reliably and validly measure behaviors ranging from indirect to direct self-harm and attempted suicide, with varying degree of frequency and severity?
 - Outcome is data from questionnaire 5S-HM (Liljedahl & Westling, 2014), ISAS (Klonsky & Glenn, 2009; Glenn & Klonsky, 2011); Swedish version of the ISAS (Lindholm, Bjärehed & Lundh, 2011) and DERS (Gratz & Roemer, 2004); Swedish version of the DERS (Friberg, 2006).

Required sample size and a priori power analyses

G*Power, 3. 1. 7 (Faul, Erdfelder, Lang, & Buchner, 2007) was used to calculate a priori power for analyzing main effects and interaction for an A X B mixed design where A is a between-subject factor with two levels (experimental and control groups) and B is a within-subjects factor with three levels (three repeated assessments). The main statistical analyses will be either mixed (within-between) Analysis of Variance (ANOVA) or Analysis of Covariance (ANCOVA), controlling for baseline. Simpler univariate analyses will be calculated, but the power analyses summarized here are for the ANOVA model.

Assuming that three effects (i.e., between levels of the factor A, within levels of the factor B and within-between interaction A X B), are of medium size ($f = 0.25$; see Cohen, 1988), a significance level is of $\alpha = .05$, and the power values of the F tests are .85, a total of $N = 98$ per treatment site must be recruited ($n=196$ including both Stockholm and Lund, whose data will be grouped and analyzed separately).

Attrition in this population based on previous studies has been estimated to be approximately 25% (Stoffers, Völlm, Rucker, Timmer, Huband & Lieb, 2012; Nadort, Arntz, Smit, Giesen-Bloo, Eikelenboom, Spirnhoven, van Asselt, Wensing, & van Dyck., 2009). In order to attain the required sample size for these power estimates, including expected attrition, a total of $N= 124$ participants is required, with $n=62$ participants in each group (treatment and control).

Significance:

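### The time-series subset is partly chosen on its own phase-A outcome, so a fall from A to B is expected without any effect of BA, and no BA-versus-TAU contrast is specified

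*Combined protocol and SAP*

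**What the plan says.** The last paragraph of Study design, just before Testing Schedule, puts two groups into the time series:

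- "All participants randomized to the intervention during the pilot phase", which means BA-arm participants only;
- people with the heaviest prior use: "10% of the individuals with the highest number of days admitted to hospital 12 months before baseline, will be selected for Time-Series Design (TS").

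Their monthly GA days form an A-B replication case series. Phase A runs "from one year ahead of assigning to the study (A") and phase B runs "during the time the participant is allocated to either BA+TAU or TAU (one year; B"). The paragraph gives no test, model or between-arm comparison for the series. Earlier in the section there is only a citation to a time-series guide.

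Three other places bear on the point:

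- Everyone enters on recent hospital use: "Admitted to hospital care for at least 7 days or presenting to the psychiatric emergency department at least 3 times during the last six months" (Patient selection criteria).
- Testing Schedule, step 7, dates baseline at randomisation for controls. For the intervention group, hospital data "are recorded with baseline date on the day for the contract".
- The sample size section says "The main statistical analyses will be either mixed (within-between) Analysis of Variance (ANOVA) or Analysis of Covariance (ANCOVA), controlling for baseline". That describes the trial's three assessments, not the monthly series.

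The documents do not mention regression to the mean.

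**The concern.** There are two separate gaps.

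**Top-10% group.** These people are picked because they had many hospital days in the year before baseline, and that year is then used as phase A. BA was not yet available to them, and the plan's definition of GA covers all other psychiatric admissions, so the selection variable and the phase-A outcome are nearly the same quantity. A high count reflects partly a lasting tendency and partly a bad year. The bad-year part is not expected to recur, so phase B should be lower on average in either arm. Replication across cases does not help, because every case picked by this rule carries the same expected fall.

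**Pilot group.** These people are not chosen by the 10% rule, but all are in the BA arm. If the recent-use entry criterion produces some fall of its own, this group has nothing to compare it with.

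Read as an ordinary A-B series, a within-person drop would mix any effect of BA with the drop due to selection. The series outcome is GA days, the subject of the primary research question, so such a drop could easily be taken as support for it.

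**Working it through.** **Inputs from the documents.** The target is 124 participants, 62 per group. The selected fraction is 10%: 0.10 × 124 = 12.4, so 12 people, about 6 per arm. The plan gives no sample size, effect or variance for the time series, so it has no figure of its own to reproduce.

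**Assumptions.** The 10% is taken from all 124, since its base is not stated. The mean is 20 or 40 hospital days a year. Between-person CV is 0.7, 1.0 or 1.5, with gamma or lognormal effects. Year-to-year correlation *r* runs from 0.3 to 0.9. BA has no effect, and whole-sample use is the same in both years.

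**Formula.** With linear regression to the mean,

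expected proportional fall = (1 − *r*) × (1 − overall mean / mean of those selected).

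The second factor is below 1, so the fall cannot exceed 1 − *r*: 30% at *r* = 0.7 and 10% at *r* = 0.9.

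**Simulation.** Yearly days were Poisson, capped at 365, around a person effect times a year effect, with the year effect tuned to the target correlation. In each of 3,000 trials per scenario, the top 12 of 124 on year A were followed into year B. There were 12 scenarios per correlation. The example columns use gamma effects, mean 20 and CV 1.0.

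| *r* | Fall across scenarios | Example, mean days A to B | Formula for the example |
|---|---|---|---|
| 0.3 | 51-60% | 103 to 46 (*r* = 0.31) | 0.69 × (1 − 20/103) = 56% |
| 0.5 | 35-43% | 86 to 52 | 0.5 × (1 − 20/86) = 38% |
| 0.7 | 20-26% | 76 to 58 | 0.3 × (1 − 20/76) = 22% |
| 0.8 | 13-17% | – | – |
| 0.9 | 6-8% | 69 to 63 | 0.1 × (1 − 20/69) = 7% |

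The example days are rounded, so percentages taken from them differ slightly from the formula. Whole-sample means were equal in A and B, so the fall comes from selection alone.

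**Two other models.**

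- Bivariate normal: the top 10% lie on average 1.755 SD above the mean, so the expected fall is 1.755 × (1 − *r*) SD. That is 1.23, 0.88, 0.53 and 0.18 SD at *r* = 0.3, 0.5, 0.7 and 0.9.
- Lognormal, mean 30, CV 1.0 or 1.5, *r* set on the log scale at the same four values: falls of 54-60%, 41-46%, 26-29% and 9-10%. In turn, 89%, 84%, 76-77% and 65% of selected people have fewer days in B than in A.

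**How often it would show.** The roughly 6 BA members have a mean fall in 93-98% of no-effect trials at *r* = 0.3 and in 68-77% at *r* = 0.9.

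**What the arm contrast does.** The BA-minus-TAU difference in A-to-B change averaged between −2.1 and +1.7 days across scenarios, so the selection effect cancels. Its SD was 6 to 83 days per person-year. The number of BA members among the 12 has a 95% range of 3 to 9.

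**Not modelled.** The effect of the entry criterion on the pilot group, because the documents give nothing to size it with.

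**The case against.** The strongest reply is that no planned conclusion depends on the series. None of the eight research questions is assigned to it, question 1 rests on medical records, and the main analysis is a randomised comparison. The plan never says that an A-to-B fall will be read as an effect of BA. Controls are already in the top-10% series, so what is missing there is one sentence. The cited time-series guide might say more about the model. The size runs from 6% to 60% depending on an assumed correlation, and it is worked out on yearly totals although the series is monthly. The pilot is meant to refine the intervention and test feasibility, for which a BA-only descriptive series is reasonable. A contrast of about 6 against 6 may be too imprecise to help.

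Much of this stands as a limit. The damage is confined to the time series, the size is not known, and the contrast is imprecise. None of it removes the defect. An A-B design exists to compare A with B, and here A is inflated by the selection rule. Having controls in the data does not help unless the plan says they will be compared. Modelling level, slope or autocorrelation within a person would not by itself remove a selection effect. An imprecise contrast that is centred correctly is safer to interpret than a within-person drop that is not.

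**Conclusion.** The concern holds. For the top-10% group, following the plan as written gives an expected fall from A to B with no effect of BA, provided that year-to-year correlation is below 1 and use is otherwise stable. The direction is secure. The size is conditional: about 6-8% of phase-A days at correlation 0.9, 20-26% at 0.7 and 51-60% at 0.3, under the assumed means and spreads. It is an expectation, and any one small set of cases may not show it. For the pilot group, the gap is the lack of a comparator, and its size cannot be determined from the documents. The randomised ANOVA or ANCOVA is not affected. The plan should be changed on this point, but the trial's main result does not depend on it.

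**What to change.** Keep the case series and prespecify three things:

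1. The series is interpreted only through the BA-minus-TAU difference in A-to-B change in monthly GA days, with a confidence interval. The top 10% is selected on the 12 months before randomisation, and assignment is the A/B boundary in both arms. This also settles the mismatch between phase A, which is defined by assignment, and the BA-arm baseline, which is dated at the contract. The population from which the 10% is drawn should be stated.
2. Pilot participants randomised to TAU are added, so that the pilot part has a comparator.
3. A sentence such as: *Within-person or within-arm falls from A to B are not evidence of an effect of BA.*

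Running the monthly series on all randomised participants is an optional alternative.

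The cost is wording and a modest extra analysis, since "Hospital data are collected monthly retrospectively from twelve months before the intervention start of the pilot" (Data collected from hospital records). There are two downsides. The top-10% contrast has about 6 people per arm and will be imprecise. Using assignment as the boundary also counts the days before the BA contract in phase B, which slightly dilutes any effect.

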The design for this project will be a Randomized Control Trial (RCT), combined with Time-series (TS; Borckardt et al, 2008). Participants will be randomized at an individual level to either BA + Treatment as Usual (TAU) or TAU. Block randomization, using tables with random numbers with blocks of four, will be used in order to minimize the confounding effect of changes in general care over time. Randomization will be stratified according to site (i.e. Lund, Malmö, Kristianstad, Helsingborg). Random number tables will be generated in SPSS. The data will be handled with Intention to treat (ITT) analysis, so that once participants are randomized, their data will be included in all analyses regardless of whether they drop-out of the study prior to its termination.

Every participant receives a consecutive research number indicating to which site they belong (Lund – L01-..., Malmö – M01 - ...; Kristianstad – K01-..., Helsingborg – H01-...). The researcher who is methodologically responsible prepares the randomization lists in four series

(one per site). The randomization numbers are named according to strata (Lund – LR01-..., Malmö – MR01 - ...; Kristianstad – KR01-..., Helsingborg – HR01-...). From the lists, a research nurse prepares four series of consecutively numbered, sealed, opaque envelopes, each containing information on which group the participant is randomized to. After inclusion in the study, the research participant is given the envelope to open. After reading, PI handles a letter containing information on which upcoming procedures for the group to which the participant has been randomized. The randomization enveloped is handled back to PI and stored in a locker, together with the master key.

In the master key, PI register the name of the participant in combination with the research code and the randomization code. Data from forms are collected online, encoded by the research number, and stored on Lund University server. These assessments will be blinded to researchers analyzing the data. Videos and audio-recordings will be stored on USB in a locker separate from the master key. Recordings will only be reviewed on computers not connected to Internet.

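### Hospital-record baseline is dated at randomisation in TAU but at the later contract day in BA, so the two arms do not share a time zero

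*Combined protocol and SAP*

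**What the plan says.** All references are to the combined protocol and SAP.

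- **TAU anchor (Testing Schedule, step 7a):** "data from hospital records for the previous 12 months, and CGI-S (Guy, 1976), are recorded with baseline date on the day for the randomization".
- **BA anchor (step 7b):** hospital records and CGI-S "are recorded with baseline date on the day for the contract (i.e. day when BA is accessible"). The length of the look-back is not restated here.
- **Order of events (steps 6, 8a, 8c):** the envelope is opened at step 6. Then "After randomization PI contacts a local RA who schedules an appointment with all participants". For BA participants the research assistant also contacts the clinician and ward staff "to schedule an appointment for negotiation resulting in a BA contract".
- **Follow-up (step 9):** for the 6- and 12-month visits, with a tolerance of 2 weeks, the collection "is repeated as baseline, with the change that the contract negotiation is replaced by contract evaluation for the intervention group". The look-back at these visits is shorter than the one in step 7a: "data from hospital records is collected from the previous 6 months".
- **Analysis set (Study design):** intention to treat; once participants are randomised, "their data will be included in all analyses regardless of whether they drop-out of the study prior to its termination".
- **Time-series subset (Study design):** besides the pilot intervention participants, it takes the top 10%, described as "the individuals with the highest number of days admitted to hospital 12 months before baseline".
- **Use of the data:** medical records answer research question 1, and the sample-size section names mixed ANOVA or ANCOVA adjusted for baseline as the main analysis.

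**The concern.** Randomisation makes the arms comparable at equal times since randomisation. Here the clock for the primary data source starts at randomisation in one arm and at a later, allocation-dependent event in the other. Four things follow.

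- GA days in the waiting period go to the pre-period in BA and to follow-up in TAU.
- If ANCOVA is used, BA's covariate includes time after randomisation, when the participant and the investigator know the allocation. TAU's covariate does not.
- If the 6- and 12-month windows run from the baseline date, BA's follow-up sits later in the course of illness than TAU's. Any trend in hospital use after entry then appears as a treatment difference.
- A BA participant who never reaches a contract has no defined baseline or windows, yet must be analysed.

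Entry requires recent heavy use (at least 7 hospital days or at least 3 psychiatric emergency visits in six months). A change in use after entry is therefore plausible, though the documents do not describe one.

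**Working it through.** **Step 1: the dates.** Step 7a gives TAU the randomisation day and step 7b gives BA the contract day. Steps 8a and 8c place the contract after randomisation, because it needs a further appointment with other parties. The section on Intervention and TAU confirms that it results from a scheduled meeting and carries three signatures. The visible text does not cap the delay, give TAU a matching delay, or say how days in the gap are handled. The mismatch therefore needs no inference.

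**Step 2: the follow-up windows.** Step 9 repeats collection as at baseline but does not name the date from which 6 and 12 months are counted. Counting from the baseline date is the natural reading, but it remains an inference. Figure 1/Bilaga 2c and the record form (Bilaga 5a) are not in the copy reviewed and could name another anchor.

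**Step 3: size.** The plan gives no figure to reproduce and no delay. I assume delays of 2, 4 and 8 weeks, which are L = 0.46, 0.92 and 1.84 months.

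*Days reassigned per BA participant* = monthly rate × L. The only hospital-day rate in the criteria is the entry threshold, 7/6 = 1.17 days per month; the emergency-visit route sets no minimum number of days.

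| Delay | At 1.17 days/month | At an assumed 1.5–2 days/month |
|---|---|---|
| 2 weeks | 0.5 | 0.7–0.9 |
| 4 weeks | 1.1 | 1.4–1.8 |
| 8 weeks | 2.1 | 2.8–3.7 |

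*Share of BA's baseline that is post-randomisation*, if its look-back is also 12 months: 2/52.18 = 3.8%, 4/52.18 = 7.7%, 8/52.18 = 15.3%. In TAU it is 0%.

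*Follow-up count with no BA effect.* The assumed GA rate at t months after randomisation is b + e·exp(−t/τ), with τ = half-life/ln 2, and is identical in both arms. TAU is integrated over 0 to 12 months and BA over L to L + 12. The grid is b = 1.5 or 2 days per month, e = ±0.5 or ±1, and half-life 1, 2 or 4 months.

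Example with b = 1.5, e = +1, half-life 2 months (τ = 2.885) and a 4-week delay:
- TAU: 18 + 2.885 × (1 − 2^−6) = 20.84 days.
- BA: 18 + 2.840 × 2^(−0.92/2) = 20.07 days.
- Difference: −0.78 days, or −3.7%.

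| Delay | Flat use | Falling use (e > 0) | Rising use (e < 0) | Absolute, either way |
|---|---|---|---|---|
| 2 weeks | 0% | −0.7 to −2.0% | +0.8 to +3.0% | 0.2–0.4 days |
| 4 weeks | 0% | −1.4 to −3.7% | +1.5 to +5.7% | 0.3–0.8 days |
| 8 weeks | 0% | −2.1 to −6.4% | +2.2 to +10.6% | 0.5–1.4 days |

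Most of the difference falls in the first window. At 4 weeks, months 0–6 are 2.0–6.4% lower or 2.7–10.6% higher, while months 6–12 are at most 1.9% lower or 2.5% higher.

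A second assumed model (decay to half the entry rate, half-life 3 or 6 months, delays of 2 to 8 weeks) gives 1.8–8.8% fewer BA days. It also gives 0 when use is flat.

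**Step 4: with a common time zero.** Setting L = 0 makes the artefact zero in every scenario. The stated sample size does not change.

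**The case against.** The best defence is that contract dating is a deliberate and sensible choice. BA cannot be used before the contract, so BA's look-back contains no BA use, and a 12-month window from the contract gives a full year of access that lines up with the 6- and 12-month contract evaluations. This is fair for a question about exposure. For an intention-to-treat comparison, though, the assigned policy begins at randomisation. A covariate that runs past known allocation in one arm only is not clean, even if treatment is not yet accessible.

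The section on Intervention and TAU says that TAU is assessed on the same schedule as the treatment group. Equal intervals can still run from different origins, and that sentence does not override steps 7a and 7b. The 2-week tolerance applies to both arms and cannot offset a one-sided shift.

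Three points stand:

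- **The sizes are assumptions throughout.** The largest rising-use figures need a starting rate of 1.5 − 1 = 0.5 days per month. That is below the 1.17 threshold rate and is reachable only through the emergency-visit route.
- **The absolute effect is small.** The largest value is 1.4 days against a 12-month base of 18–24 days. If the SD is at least 18 days (an assumption; none is given), that is at most about 1.4/18 = 0.08 SD. The trial is powered for f = 0.25, which is d = 0.5 with two groups.
- **The problem is recoverable**, because the records are retrospective and the randomisation is logged.

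**Conclusion.** The concern holds. Confidence is high that steps 7a and 7b give hospital records an arm-specific time zero, and that post-randomisation GA days therefore enter the baseline in BA only. The gap for BA participants who never sign a contract also follows from the text. The shift of the follow-up windows is an inference from step 9, and every size depends on assumed delays and trajectories. The effect is nil with flat use, favours BA if use falls after entry, and works against BA if it rises. Over the assumed range it is 0.2–1.4 days in 12 months. This is unlikely to decide the trial alone, but it is an avoidable one-sided artefact in the primary data source. It should be fixed, and the anchor declared, before analysis.

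**What to change.** In steps 7b and 9, make the randomisation date time zero for hospital records in both arms in the primary intention-to-treat analysis. It should govern the 12-month pre-period, the 0–6 and 6–12 month windows, the ANCOVA baseline and the top-10% time-series selection. State the look-back length in 7b. Include BA participants without a contract on the same dates. Record the contract date, report the randomisation-to-contract delay, and keep contract-day dating as a sensitivity analysis.

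The A-B time series may start phase B at the contract day if the plan says so, since its present anchor (assignment to the study) is not defined. CGI-S ratings should not be re-dated; report their timing relative to randomisation by arm. Check Figure 1/Bilaga 2c and Bilaga 5a for a conflicting anchor.

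The cost is a wording change plus re-cutting BA windows from the randomisation log. If only monthly counts were stored, BA records may need re-extraction. Record windows in BA would no longer coincide with the contract evaluations. With a 2-, 4- or 8-week wait, BA's 12-month window would hold about 50, 48 or 44 weeks of access instead of 52, which is normal under intention to treat and should be reported.

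### Baseline self-report outcomes (questions 2, 3, 5 and 6) are collected after the participant knows the allocation, so the baseline used in the analysis may be affected by it; baseline CGI-S (question 4) is post-allocation in BA and of uncertain order in TAU

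*Combined protocol and SAP*

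**What the plan says.** All steps cited are in the Testing Schedule of the combined protocol and SAP.

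- **Step 5, before allocation:** the PI administers M.I.N.I., SCID II, Fem frågor, AUDIT and DUDIT. None of these is the outcome for questions 2-6.
- **Step 6, allocation:** "PI provides a consecutively numbered randomization envelope which the participant opens and signs". Depending on the group, "a sheet providing information on the study is given and explained".
- **Step 7, baseline by the PI:** hospital-record data and CGI-S. In the control group they "are recorded with baseline date on the day for the randomization"; in the intervention group they "are recorded with baseline date on the day for the contract".
- **Step 8a, baseline by the research assistant (RA):** "After randomization PI contacts a local RA who schedules an appointment with all participants, and administers a link to the self-administered forms". The forms are 5S-HM, WHODAS 2.0, Brief COPE, DERS and ISAS. No maximum interval from the envelope is given.
- **Step 8b:** "RA is available for the individual and provides help if necessary, when completing the forms online". The section on the intervention and TAU says that the local RA also acts as BA nurse clinician and signs the BA contract.
- **Step 9:** collection at 6 and 12 months "is repeated as baseline, with the change that the contract negotiation is replaced by contract evaluation for the intervention group".

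The section linking methods to research objectives assigns WHODAS 2.0 to question 2, Brief COPE and DERS to question 3, CGI-S to question 4, 5S-HM and ISAS to question 5, and 5S-HM to question 6. Question 1 rests on medical records. The sample-size section plans a mixed ANOVA over three assessments, or ANCOVA adjusted for baseline. The only blinding stated, under Study design, concerns those who analyse the data.

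**The concern.** A baseline covariate should be something that allocation cannot have touched. Here a participant rates functioning, coping, emotion regulation and self-harm already knowing whether BA has been granted or withheld. Relief, disappointment or a wish to justify the allocation could all move the answers. Help comes from a person who, for the BA arm, is also part of the intervention. Blinding the analysts does not protect a self-report by someone who knows the arm.

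There is a second route. Study design promises to analyse everyone randomised, but a person lost between the envelope and the RA appointment has no baseline on these five forms, and such losses could differ by arm.

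At stake is the interpretation of the secondary questions, not the primary one.

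**Working it through.** **1. Order of events.** For the five forms the text is explicit: envelope at step 6, forms after randomisation at step 8a. No readable passage gives an earlier measurement of them.

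For CGI-S the arms differ. In BA it is dated to the contract, which cannot precede allocation. In TAU only the day of randomisation is fixed. List order does not settle the hour, because the list is not strictly chronological: step 7b is dated to a contract that is negotiated only at step 8c. The schedule figure could not be read ("For a visual description of the testing schedule, please see Figure 1, Bilaga 2c").

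**2. Scale.** The plan gives no figure on this point. Its N = 98 is reproduced by the between-group F test with f = 0.25, three assessments, alpha 0.05 and an assumed correlation of 0.5, which the plan does not state: noncentrality 0.25² × 98 × 3 / (1 + 2 × 0.5) = 9.19 on 1 and 96 df, power 0.851. For two equal groups f = 0.25 is d = 2 × 0.25 = 0.5 SD. Changing the order of the forms does not alter N.

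**3. Bias formulas.** Work in SD units with no true effect. Let s be the allocation-induced baseline shift in BA relative to TAU (positive = BA looks better), p the fraction of s still present at follow-up, and rho the baseline/follow-up correlation. None of the three is in the documents.

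- Unadjusted follow-up: p·s
- Change from baseline: p·s - s = s(p - 1)
- ANCOVA: p·s - rho·s = s(p - rho)
- Between-group mean over three assessments: (s + 2p·s)/3 = s(1 + 2p)/3

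**4. Illustration.** Assumed s = 0.1 to 0.3 and rho = 0.3 to 0.7:

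| p | ANCOVA | Change | Unadjusted | Mean of three |
|---|---|---|---|---|
| 0 | -0.21 to -0.03 | -0.30 to -0.10 | 0 | +0.03 to +0.10 |
| 0.5 | -0.06 to +0.06 | -0.15 to -0.05 | +0.05 to +0.15 | +0.07 to +0.20 |
| 1 | +0.03 to +0.21 | 0 | +0.10 to +0.30 | +0.10 to +0.30 |

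All signs reverse if s is negative. The largest ANCOVA figure is 0.21/0.5 = 42% of the planned effect; at p = rho the ANCOVA bias is zero. A simulation with 46 per arm (62 × 0.75 = 46.5, rounded down), s = 0.3, rho = 0.5 and p = 0 gave -0.149, -0.296, -0.003 and +0.095, against -0.15, -0.30, 0 and +0.10 from the formulas.

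**5. Could the trial's data reveal the shift?** With 62 per arm the SE of a baseline difference is sqrt(2/62) = 0.180 SD, and 1.96 × 0.180 = 0.352. Two-sided 5% power is 0.086, 0.200 and 0.386 for s = 0.1, 0.2 and 0.3. An unremarkable baseline table would not be reassuring.

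**6. What a pre-allocation baseline changes.** The baseline shift becomes zero, while an expectation effect p·s may remain at follow-up. ANCOVA, change and unadjusted follow-up then all carry p·s; the mean over three assessments carries 2p·s/3. With s = 0.3 and p = 0.5 that is 0.15 for the first three and 0.10 for the fourth.

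**7. Calendar.** Active data collection runs 36 months from March 2016, to March 2019. If that includes 12-month follow-up, the last baseline falls about March 2018, before this version (April 2018). The text does not say whether it does.

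**The case against.** **The effect is hypothetical.** This stands as to size: s, p and rho are all assumed, the ANCOVA range passes through zero, and one range for several instruments is a simplification (an ISAS item such as age of onset may hardly move). The ordering itself does not depend on those assumptions.

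**A pre-allocation baseline may increase the net ANCOVA bias.** If expectation effects at follow-up count as bias, p·s exceeds the present s(p - rho) in absolute size whenever p > rho/2, that is, above 0.15 to 0.35 for rho of 0.3 to 0.7. This is correct. But the present cancellation is accidental and depends on quantities nobody knows. In the same setting (s = 0.3, rho = p = 0.5) ANCOVA is unbiased while change from baseline is off by -0.15. It also does nothing about losses before baseline.

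**Recruitment may be over.** On one reading of the calendar, reordering reaches nobody. This limits the practical value of the first part of the fix, not of the reporting part.

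**The plan already mentions simpler univariate analyses.** These might include an unadjusted follow-up comparison, but the sentence is too general to tell. Such a comparison could not show which estimate is right.

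**Stronger readings a reader might infer.** One is that CGI-S is post-allocation in both arms; the TAU text fixes only a day, and the PI, who performs steps 5 to 7, could have rated it before the envelope. Another is that the ordering inflates the apparent benefit of BA; the documents give no direction. A third is that the primary result is compromised; it comes from medical records.

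**Conclusion.** The point holds for the five self-report forms: their baseline is post-allocation by the plan's own schedule, in both arms, and may be affected by allocation in unknown size and direction. For CGI-S it holds in BA and is uncertain in TAU. Confidence is high on the ordering for the five forms and low on the consequence, since every bias figure is an illustration under assumed s, p and rho.

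It would be too strong to say that moving the baseline makes all contrasts agree or removes the bias. It makes ANCOVA, change from baseline and unadjusted follow-up target the same quantity, but not the mean over three assessments. In an open trial it leaves expectation effects at follow-up untouched. The point is worth correcting because it affects the interpretation of five secondary questions and the correction is cheap.

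**What to change.** **Participants not yet randomised.** Complete the step 8a forms and CGI-S after step 5 and before the envelope, in both arms, with one CGI-S dating rule. State the date from which the 6- and 12-month windows run for these measures. The hospital-record baseline can keep its own date.

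**Participants already enrolled under the present order.** Report baseline scores by arm and losses between envelope and baseline by arm. State that the baseline was post-allocation when interpreting questions 2-6, and for CGI-S in TAU say when it was actually rated if that is known. An unadjusted 6- and 12-month comparison is optional. Its SE is 1/sqrt(1 - rho²) times that of ANCOVA, so 5%, 15% or 40% larger at rho of 0.3, 0.5 or 0.7.

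**Cost.** The first part uses the same forms and staff. It brings a slightly longer assessment before randomisation, a few people assessed but never randomised, an ethics submission, and two baseline definitions if enrolment is ongoing. If follow-up is counted from the contract, the BA interval from forms to follow-up grows by the wait from envelope to contract, which the documents do not give. The first part may reach few participants, or none. The reporting part needs no new data and may carry most of the practical value.
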